## **Bowel Preparation and Sedation**

Patients will be instructed to eat low-residual foods for two days before colonoscopy. Oral and written instructions on the split-dose bowel preparation of 3 L polyethylene glycol will be provided. Colonoscopy will be performed with moderate sedation using intravenous fentanyl plus midazolam.

## **Colonoscopy Procedures**

Colonoscopies will be performed by two board-certified colonoscopists who

have experience in WE ([name], [name]). The colonoscopist is blinded as to whether water or mixed saline/water is being used. Standard colonoscopes (CF-Q260AL/I, CF-HQ290L/I; Olympus Medical Systems Corp., Tokyo, Japan) will be used.

Antispasmodic medication will be administered during colonoscopy examination if indicated. All infused fluids will be warmed to approximately 32-33 °C. CO2 insufflation will be used for CO2 group and during the withdrawal phase of the WE group. Colonoscopy will begin with the patients in the left lateral position. In the WE group, the air pump will be turned off before starting the procedure. During the insertion phase, air and residual water or feces in the rectum will be aspirated, and then the colon will be irrigated with warm fluid using a flushing pump (Olympus AFU-100; Olympus Corp.). There will be no restriction placed on the overall volume of fluid infused to achieve adequate cleansing. WE entails the infusion of fluid to open the lumen and suction of infused fluid sequentially. Air pockets, when encountered, will be aspirated. When the cecum is reached and after most of the fluid is suctioned to collapse the cecal lumen, CO2 will be opened. Cecal intubation will be defined as the passage of the scope tip beyond the ileocecal valve with visualization of the medial wall between the ileocecal valve and the appendix orifice.

Polyp search and resection will be performed during the withdrawal phase in all groups. Insertion polypectomy will not be performed. All proximal colon (defined as the colon segment proximal to the descending colon) polyps will be removed irrespective of their size and appearance. All diminutive polyps with hyperplastic appearance (based on narrow band imaging) in the rectosigmoid colon will be documented by photography and left alone. Polyp size will be determined by comparison with an opened biopsy forceps or a snare.

In all groups, the following information will be recorded: bowel preparation quality using the Boston Bowel Preparation Scale score; the total amount of sedative medications; the length of colonoscopy reaching cecum; the amount of fluid infused and suctioned during insertion and withdrawal phases; the insertion time; the withdrawal time; the need of abdominal compression and/or position change to assist colonoscopy insertion; and the overall polyp number,

size, histology and location.

### **Mucus scores**

During the withdrawal phase of the colonoscopy, the blinded colonoscopist and another blinded research assistant will grade the amount of mucus produced in the left colon (descending colon, sigmoid colon, rectum) independently. No validated scoring system for the mucus production in the colon is available. We use a 5-point Colon Mucus Scale (CMS) (0-4 points), modified from the original colon mucus study by El Rahyel et al., to quantitate the amount of mucus production in left colon: score 0: no visible mucus; score 1: minimal amounts of clear mucus in thin streaks or strands; score 2: mild opaque mucus in thin strands; score 3: moderate opaque mucus in thicker clumps covering one side of surface; score 4: more opaque mucus in thicker clumps covering more views of lumen (Figure 1). Prior to beginning scoring, the colonoscopists and study assistant will review 10 videos and discuss their scores. After they have reached consensus on the 10 cases, scoring will be performed independently.

### **Outcomes**

The primary outcomes are the left colon mucus scores using CMS between colonoscopy using CO2 insufflation and WE, and, in those patients undergoing WE, the scores between groups using water versus 50% saline versus 25% saline. Secondary outcomes include procedure times (insertion and withdrawal times) and acute serum electrolyte abnormality in the WE saline groups. Patients assigned to the WE saline groups will receive measurements of the serum sodium, potassium, and chloride, which will be performed 20 minutes before and 60 minutes after the colonoscopy.

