### **Sample size estimation**

We performed an observational study focusing on left colon mucus production using CMS scoring system by unblinded colonoscopist and compared either full strength normal saline (normal saline group), 1:1 mixed normal saline/water (50% saline group), or 1:3 mixed normal saline/water

(25% saline group) during WE insertion in patients undergoing routine colonoscopies in December 2020. We compared these findings with the reference WE water group which was video recorded during our previous randomized controlled trial comparing right colon adenoma miss rate using WE and CO2 insufflation. The results showed that fluid containing saline significantly reduced the mucus production compared to water alone (Table 1).

The sample size estimation is based on the assumption that WE 50% saline infusion will reduce left colon mucus score compared to WE water infusion. Mucus score reduction to  $\leq 1$  is considered clinically significant. According to our preliminary data, we estimate the proportion of subjects with CMS score  $\leq 1$  to be 50% in the WE water group. The sample size needed to show the proportion of subjects with CMS score  $\leq 1$  that can be increased to 80% by WE 50% saline infusion at a 5% alpha error level with 90% power will be 68 patients per group. To account for dropouts, incomplete procedures, and inadequate preparation, an additional 10% will be enrolled. Therefore, a total of 300 patients (75 patients in each group) will be enrolled.

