### **Statistical analysis**

Categorical variables will be presented as numbers (percentages), whereas continuous variables will be expressed as the means  $\pm$  standard deviations. Overall *P* values for categorical and continuous parameters will be obtained by Fisher's exact test and Kruskal-Wallis test, respectively. Pairwise comparisons among all groups were performed when the overall group effect was significant. Agreement between the blinded raters will be tested with Fleiss kappa. For mucus production quantity, the 2-category scale (minimal [score 0-1] vs. moderate [score 2-4]) will be examined. Potential risk factors for mucus production include female sex, lower body mass index, prior abdominal or pelvic surgery, poor bowel preparation, water as the infused solution, larger volume of infusion, and longer insertion time. Univariate and multivariate logistic regression analyses will be used to assess which of the demographic and procedural data are independent predictors of moderate mucus production. Factors with a *P* value  $< 0.1$  on univariate analysis will be further entered in the multivariate logistic regression analysis. The odds ratio with 95% confidence

interval will be used to describe the influence of various factors on mucus production. All statistical analyses will be performed by using SAS version 9.3 or later (SAS Institute Inc., Cary, NC, USA). The criterion for statistical significance will be a *P* value <0.05.

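### The endpoint and contrast the trial is powered on (CMS ≤1, WE 50% saline versus WE water) are not the outcomes declared primary, and the plan does not say which test decides

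*Combined protocol and SAP*

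**What the plan says.** Three sections of the combined protocol and SAP bear on this.

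- **Outcomes** declares the score primary: "The primary outcomes are the left colon mucus scores using CMS between colonoscopy using CO 2 insufflation and WE". It continues, for patients having WE, with "the scores between groups using water versus 50% saline versus 25% saline". No threshold is mentioned.
- **Sample size estimation** begins from a score reduction ("The sample size estimation is based on the assumption that WE 50% saline infusion will reduce left colon mucus score compared to WE water infusion") but calculates on a threshold: "The sample size needed to show the proportion of subjects with CMS score" of 1 or less. The control rate is taken "to be 50% in the WE water group", a rate "that can be increased to 80% by WE 50% saline infusion", and the requirement "at a 5% alpha error level with 90% power will be 68 patients per group". The section describes reaching 1 or less as the clinically significant result.
- **Statistical analysis** assigns Fisher's exact test to categorical variables and Kruskal-Wallis to continuous ones, with pairwise tests after a significant overall result. It adds: "For mucus production quantity, the 2-category scale (minimal [score 0-1] vs. moderate [score 2-4]) will be examined". One threshold, P<0.05, applies throughout. No primary test is named, score and proportion are not ranked, and no adjustment is given.

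**The concern.** The score and the proportion measure different things. The score also responds to movement between 0 and 1, and between 2 and 3–4, none of which changes whether a patient is at CMS ≤1. The comparisons differ too: Outcomes lists CO2 versus WE and a three-way WE comparison, while the sample size addresses one pair of arms.

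With neither form nor contrast ranked, a reader cannot tell in advance which P value decides the trial. The choice could be made after the data are seen. A trial could also be called positive on the declared primary outcome with no gain on the criterion the plan itself calls clinically significant.

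**Working it through.** **1. The sections side by side**

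| Section | Form | Comparison | Alpha and power |
|---|---|---|---|
| Outcomes | CMS score, 0–4 | CO2 vs WE; water vs 50% vs 25% saline | none attached |
| Sample size estimation | proportion with CMS ≤1 | 50% saline vs water | 5%, 90% |
| Statistical analysis | 2-category form by name; score by inference | all groups, then pairwise | P<0.05 throughout |

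The Kruskal-Wallis test for the score is an inference. The plan gives that test for continuous variables, which it summarises by mean and SD, and Table 1 reports the score as mean (SD).

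**2. The plan's own figure.** Inputs from Sample size estimation: 50% vs 80%, alpha 5%, power 90%. Sidedness is not stated; two-sided is assumed. The mean proportion is 0.65.

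n = [1.960·√(2·0.65·0.35) + 1.282·√(0.5·0.5 + 0.8·0.2)]² / 0.30² = 51.01, so 52 per group.

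With continuity correction: (51.01/4)·[1 + √(1 + 4/(51.01·0.30))]² = 57.5, so 58.

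The stated 68 is not reproduced, but the difference is conservative. It is a separate matter from this point.

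**3. Power at 68 per arm**

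- *Proportion, 50% vs 80%:* Φ[(0.30·√68 − 1.960·√0.455)/√0.41] = 96.4%. Exact power of Fisher's test is 95.0%.
- *Score, Table 1 means 1.88 and 0.94, SDs 0.78 and 0.66 (normal approximation):* n = (1.960 + 1.282)²·(0.78² + 0.66²)/0.94² = 12.4, so 13 per group. Power at 68 exceeds 99.9%. Table 1 is an unblinded comparison with 17 patients per arm, so this is only a rough guide.

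**4. False positives from having two forms.** The documents give no score distribution for planning, so one is assumed: 15/35/30/15/5% at scores 0 to 4, equal in four arms of 68, with 10,000 simulated trials. Kruskal-Wallis was significant in 4.6%, the 2-category test in 4.8% (chi-square standing in for Fisher), and at least one in 6.7%. Repeat runs with this mix and with 15/40/33/10/2% gave about 6–7%. For two arms, at least one test was significant in 5.8%. These figures cover the two forms only, not the number of comparisons.

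**5. Disagreement at the planned effect.** Assumed mixes: 15/35/30/15/5% (50% at ≤1) vs 30/50/13/5/2% (80% at ≤1), 68 per arm. Score test 95.3%, Fisher 95.0%, at least one 97.3%. Disagreement = 2·97.3 − 95.3 − 95.0 = 4.3%. Other assumed splits gave 3–7%, with power of about 90–98% for either form.

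**6. A shift only between scores 0 and 1** (both arms 50% at ≤1, 68 per arm; percentages for scores 0 to 3)

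| Assumed mixes | Score test significant | Fisher on CMS ≤1 significant | Disagree |
|---|---|---|---|
| 10/40/40/10 vs 35/15/40/10 (25 points) | 27–28% | 3% | 27–28% |
| 10/40/40/10 vs 20/30/40/10 (10 points) | 8% | 3% | 7–8% |

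**7. An instance in the pilot data.** Table 1's n, mean, SD and count at ≤1 fix the score counts: normal saline 11/6/0/0/0, and 50% saline 4/10/3/0/0. Kruskal-Wallis on these gives P=0.009. Fisher on 17/17 vs 14/17 gives P=0.23. Full-strength saline is not an arm of this trial, so this shows only that the two forms can part.

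**The case against.** The strongest reply is that the plan can be read coherently. The only sentence specific to mucus in Statistical analysis uses the cut at 0–1 versus 2–4, the same cut as in the sample size section. The two sections together could be taken to define what Outcomes means by mucus scores. This narrows the ambiguity but does not close it: the form is only to be examined, the passage goes on to logistic regression, and nothing withdraws the score or names the contrast.

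It can also be said that the choice matters little. In Table 1 the mean score and the proportion at ≤1 move in the same order across all four fluids (0.35 and 100%, 0.94 and 82%, 1.06 and 77%, 1.88 and 24%), and the 25-point shift in step 6 was constructed to be extreme. Both points stand, and they limit the size of the problem.

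Third, the Background states the hypothesis in scores, and dichotomising discards information. Keeping the score primary and restating the power for it would also be coherent. That is fair; the fix below is preferred because it follows the plan's own power calculation and its own statement of clinical importance.

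A reader might infer more than the text supports:

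- *That the plan names two rival primary outcomes.* It does not; no section calls the proportion primary.
- *That the stated power belongs to no endpoint.* It belongs to one explicit endpoint and contrast, which are not those declared primary.
- *That two tests at 5% give nearly 10%.* The figure for independent tests is 1 − 0.95² = 9.75%, but these two tests use the same data and are strongly correlated.
- *That the trial is underpowered for the score.* Steps 3 and 5 do not support this.

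**Conclusion.** The point holds as a mismatch of both endpoint and contrast, with no ranking to resolve it. The main harm is a success criterion left open to choice after the results. It should be corrected before analysis, but its numerical effect is modest: about 1–2 percentage points of added false-positive risk from the two forms, and disagreement in about 3–7% of trials at 50% versus 80%. Larger disagreement needs a sizeable movement between scores 0 and 1 with none across the cut.

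These sizes rest on assumed score distributions, 68 evaluable patients per arm, two-sided 5% tests, and Kruskal-Wallis being the intended test for the score. The mismatch itself rests on the text alone.

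**What to change.** In Outcomes, name the proportion with CMS ≤1, WE 50% saline versus WE water, as the primary endpoint and contrast, matching Sample size estimation. In Statistical analysis, state that the primary conclusion rests on that one test, and whether it is run directly or only after a significant four-group test. Make the 0–4 score analysis supportive, and CO2 versus WE and the remaining WE comparisons secondary. Naming the form without the contrast would not be enough, because the primary conclusion would still have no single test.

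The cost is wording in two sections. Sample size, data collection and procedures do not change, and under the plan's own assumptions power at 68 per arm is 95–96%. The downside is that a result seen only on the full score, or only in another contrast, can no longer be called primary.

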### **Sample size estimation**

We performed an observational study focusing on left colon mucus production using CMS scoring system by unblinded colonoscopist and compared either full strength normal saline (normal saline group), 1:1 mixed normal saline/water (50% saline group), or 1:3 mixed normal saline/water

(25% saline group) during WE insertion in patients undergoing routine colonoscopies in December 2020. We compared these findings with the reference WE water group which was video recorded during our previous randomized controlled trial comparing right colon adenoma miss rate using WE and CO2 insufflation. The results showed that fluid containing saline significantly reduced the mucus production compared to water alone (Table 1).

The sample size estimation is based on the assumption that WE 50% saline infusion will reduce left colon mucus score compared to WE water infusion. Mucus score reduction to  $\leq 1$  is considered clinically significant. According to our preliminary data, we estimate the proportion of subjects with CMS score  $\leq 1$  to be 50% in the WE water group. The sample size needed to show the proportion of subjects with CMS score  $\leq 1$  that can be increased to 80% by WE 50% saline infusion at a 5% alpha error level with 90% power will be 68 patients per group. To account for dropouts, incomplete procedures, and inadequate preparation, an additional 10% will be enrolled. Therefore, a total of 300 patients (75 patients in each group) will be enrolled.

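### The 68 per group does not follow from the stated inputs, which give 48 to 58, and the 50% control rate credited to preliminary data is 4/17 (24%) in Table 1.

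*Combined protocol and SAP*

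**What the plan says.** Under Sample size estimation, the calculation concerns one pair, WE water against WE 50% saline, on the proportion with a CMS score of 1 or less. The water rate is introduced with "According to our preliminary data, we estimate the proportion of subjects with CMS score" ≤1 "to be 50% in the WE water group". The target is a proportion "that can be increased to 80% by WE 50% saline infusion", and the resulting size is given as "by WE 50% saline infusion at a 5% alpha error level with 90% power will be 68 patients per group". A further 10% is then added, giving 75 per group and 300 in total. The section names no formula or test for the calculation, and does not say whether it is one- or two-sided.

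The preliminary data are in Table 1: 17 patients per arm, scored unblinded, with the comparator being a "reference WE water group which was video recorded during our previous randomized controlled trial". The table shows CMS ≤1 in 4 (24%) of the water patients and 14 (82%) of the 50% saline patients.

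Under Statistical analysis, Fisher's exact test is named for overall comparisons of categorical variables. On the next step the text reads "Pairwise comparisons among all groups were performed when the overall group effect was significant", and on the threshold "The criterion for statistical significance will be a *P* value <0.05". No adjustment for multiple comparisons is stated.

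**The concern.** This is the trial's only justification of its size. It states two rates, an alpha and a power, and allocation is equal, so 68 should be recoverable by a standard two-proportion calculation. It is not. Either the stated power is wrong, or an input that the text omits, such as a smaller alpha, was used. The distinction matters: if a multiplicity-adjusted alpha produced 68, the Statistical analysis section should apply the same alpha to the pairwise tests, and it applies an unadjusted 5%.

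The control rate has a separate problem of traceability. The 80% target agrees with Table 1 (82%), but the 50% control rate is credited to the same data, which show about half that rate.

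Finally, the stated power treats the pair as a stand-alone test, whereas the analysis plan reaches the pair only after a significant four-group test. Power under that rule depends on the 25% saline and CO2 rates, and the sample size section assumes neither.

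**Working it through.** **Inputs.** From Sample size estimation: p1 = 0.50, p2 = 0.80, alpha 0.05, power 0.90. Allocation is equal (Randomization). Two-sided testing is my assumption, since sidedness is not stated; one-sided is also tried. So z(α/2) = 1.960, z(β) = 1.2816, difference d = 0.30, mean rate 0.65, and p1q1 + p2q2 = 0.25 + 0.16 = 0.41.

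**Attempt to reproduce 68 (per group, two-sided 5%, 90% power).**

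- Unpooled variance: (1.960 + 1.2816)² × 0.41 / 0.09 = 47.9, so 48.
- Pooled variance under the null: [1.960 × √(2 × 0.65 × 0.35) + 1.2816 × √0.41]² / 0.09 = (1.3221 + 0.8206)² / 0.09 = 51.01, so 52.
- Pooled with continuity correction: (51.01/4) × [1 + √(1 + 4/(51.01 × 0.30))]² = 57.5, so 58.
- Exact Fisher test by full enumeration: power 0.8996 at 57 and 0.906 at 58, so 58.
- The arcsine formula gives 51. A less usual form, with variance 2 × 0.65 × 0.35 throughout plus continuity correction, gives 60.

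One-sided 5% gives about 40 to 50 over the same formulas, further from 68. Dropout is not the explanation, because the 10% is added afterwards: 68 × 1.10 = 74.8, rounded to 75, and 4 × 75 = 300. That part is consistent.

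**Power for the single pair, exact Fisher, two-sided 5%.**

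| n per group | Power |
|---|---|
| 58 | 90.6% |
| 68 | 95.0% |
| 75 | 96.5% |

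**What would give about 68.** At 90% power, alpha 0.05/3 gives 66 (pooled), and alpha 0.05/2 with continuity correction gives 67. At 95% power and two-sided 5%, the continuity-corrected formulas give 66 to 70. None of these inputs is stated.

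**Control rate.** Table 1 gives 4/17 = 23.5%, Clopper-Pearson 95% CI 6.8% to 49.9%; the planned 50% lies just outside it. With 4/17 against 80% at two-sided 5% and 90% power, the same three formulas need 12 (unpooled), 15 (pooled) or 18 (continuity-corrected) per group.

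**Power under the overall-test-first rule.** This was simulated with 300,000 trials per scenario. Success required a significant exact 2×4 Fisher test and then a significant water versus 50% saline Fisher test in the expected direction, each at 5%. Fisher's test for the pair is an assumption, because the pairwise test is not named. The rates in the other two arms are also assumptions.

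| Other two arms | n = 58 | n = 68 | n = 75 |
|---|---|---|---|
| 66% and 66% (about least favourable) | 82.7% | 89.0% | 92.2% |
| 80% and 80% | 89.6% | 94.5% | 96.2% |
| 80% and 90% | 90.5% | 95.0% | 96.5% |

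The 89.0% is close to the stated 90%, but the protocol makes no such assumption, so it does not account for the 68.

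**The case against.** The strongest reply is that nothing is at risk. Both discrepancies err towards more patients: 68 exceeds what the inputs require, and a 50% control rate asks for far more patients than 24% would. The pair has about 95% power at 68 and 96.5% at 75, so this is a matter of reporting. That stands, and it limits how much weight the point carries.

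A second reply is that 50% is a sensible planning value. The text calls it an estimate, and it is almost exactly the upper confidence limit of 4/17. The data come from 17 patients per arm, scored unblinded, with a historical video comparator. All this is fair, but the protocol gives none of these reasons. The defect is a missing justification and a wrong attribution, not a wrong rate.

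Third, the overall-test-first figures depend on assumed rates, and the 66% scenario is pessimistic beside the 13/17 (77%) that Table 1 shows for 25% saline. With that arm set at 77% and CO2 varied from 30% to 95%, an approximate simulation (chi-square for the overall test) gave 93.0% to 95.0% at 68. Even the least favourable case above has 92.2% at 75. The rule therefore reveals no shortfall if all 75 per arm are analysed; the remaining point is that the stated power does not describe the planned procedure.

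**Conclusion.** The concern holds. The stated inputs require 48 to 58 per group by the usual two-sided methods, not 68, and 68 corresponds to about 95% power by exact Fisher for the single comparison. This rests on two-sided 5% without an alpha adjustment; one-sided testing widens the gap. The 50% water rate is credited to preliminary data that show 4/17 (24%), with no reason given. Both errors are conservative for the sized pair, so the planned 300 patients are adequate for it on the stated rates. The text should nevertheless be corrected: its power figure is wrong as written unless an unstated input was used, and only the sponsor can say which.

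**What to change.** Keep 75 per arm and amend the text of Sample size estimation:

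1. State the test or formula, the sidedness and the alpha actually used.
2. Give the power at 68 as about 95% for the single WE water versus WE 50% saline comparison at two-sided 5%. Restating the required number as about 58 is also arithmetically correct, but it sits awkwardly with the overall-test-first rule, under which 58 gives 82.7% to 90.5% in the scenarios above.
3. Add that power under the overall-test-first rule depends on the 25% saline and CO2 rates (about 89% to 95% at 68 in those scenarios), and state the rates assumed.
4. Report the preliminary water rate as 4/17 (24%) and give the actual reason for planning on 50%, or stop attributing 50% to those data.
5. If an adjusted alpha was used to reach 68, state it and apply the same alpha in Statistical analysis.

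The cost is a few sentences. Enrolment does not change, and the analysis changes only if item 5 applies.
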